### **Inflammatory cytokines**

Before and at approximately 1, 1.5, 2, 3, and 4 hrs after endotoxin administration all subjects will have an 10 ml blood sample drawn for plasma levels of inflammatory cytokines (including but not limited to: IL-1beta, IL-4, IL-6, TNF alpha, IL-10, IL-12). In addition, plasma levels of inflammatory cytokines will be measured just prior to subsequent PET scans following LPS administration for Aim 5.

### **Specimen Storage**

Specimens will be logged into a specimen tracking log and stored either at the PET Center or YCCI Biorepository. This log will include Study ID, date drawn, label of specimen (i.e. barcode, type of specimen etc), location, and date withdrawn for analysis or destruction.

#### **Behavioral Measures**

We will assess PTSD, depression and anxiety symptoms on all subject participation days with the Civilian M-PTSD, Montgomery-Åsberg Depression Rating Scale (MADRS) (112) and Hamilton Anxiety Rating Scale (HARS) (113) respectively and explore relationships between these measures and radiotracer binding in relevant brain regions.

## General Assessments may include:

1). Socio-demographic/General Information: At intake, demographic data and medical history will be assessed with interviews and self-report forms that provide data on age, race, socioeconomic status, marital status, educational and occupational levels, and significant medical history. These are adapted from previous diagnostic and clinical studies at this center.

2) The Structured Clinical Interview for DSM-V (SCID-5) will be used to provide current and past diagnoses of substance use and other psychiatric disorders.

3) *SCID II* is an addendum to the SCID that is used to diagnose axis II disorders including Antisocial Personality Disorder.

4) Civilian M-PTSD is an assessment of symptoms of posttraumatic stress disorder.

5.) *Health Status* is a self-report instrument that will be used to assess the lifetime occurrence of illnesses or conditions.

6.) *Concomitant Medication Log* will be used scan day to determine what medications have been taken in the last two weeks.

7.) *Bower VAS and the endotoxin symptoms checklist* will be administered to participants during the endotoxin challenge.

### **Medical Assessments**

Any clinically significant abnormal medical screening laboratories from the initial assessment will be repeated prior to each imaging session.

1) Physical exam by a state licensed physician or Advanced Practice Registered Nurse

2) Laboratory Blood Tests including a complete blood count with Diff, blood urea nitrogen, creatinine, fasting blood sugar, electrolytes, liver function tests, thyroid function tests (including T3, T4, T3RU, estimated free T4), thyroid stimulating hormone levels and coagulation panel, and DNA genetics testing. For all laboratory screening blood and urine tests, one of the study physicians reviews the labs, and in combination with the results from the physical exam, decides if the subject is sufficiently healthy (so that it does not alter the scientific integrity of the study, or risk to the subject for study participation) to participate in the study.

3) *Urine toxicology screens* may be performed at baseline, prior to PET imaging, and more frequently if the clinician or research staff become concerned about possible illicit drug use. Patients will be instructed that random urine drug screens will be performed. Urine samples may be tested for amphetamines, barbiturates, benzodiazepines, cannabinoids, cocaine, and opiates.

4) *Pregnancy Tests* female patients will have a blood pregnancy test at baseline and also a urine pregnancy test on the day of each PET scan and MRI scan.

### **Cognitive Measures**

We may obtain these measures at baseline and up to two times on the PET days.

**1. Cogstate Battery (30 minutes)** – This computerized test battery will assess memory and cognition. The tasks may include:

Page 12 of 45

- a. International Shopping List Task a computerized task to assess verbal learning and memory.
- b. Groton Maze Learning Task a computerized task to assess executive function and spatial problem solving.
- c. Detection Task a computerized task to assess psychomotor function and speed of processing.
- d. Identification Task a computerized task to assess visual attention and vigilance.
- e. One Card Learning Task a computerized task to assess visual learning and memory.
- f. One Back/Two Back Tasks computerized tasks to assess attention and working memory

*Probabilistic Reward Task*: The PRT has been successfully used to assess reward responsiveness (114-116). In each trial, subjects choose which of two difficult-to-differentiate stimuli was presented. Stimuli consist of simple cartoon faces (diameter: 25 mm; eyes: 7 mm) presented in the center of the monitor. At the beginning of the trial, the face has no mouth. After a given delay, either a straight mouth of 11.5 mm ("short mouth") or 13 mm ("long mouth") is presented for 100 ms. Subjects are instructed to press an appropriate button to decide whether a long or small mouth had been presented. Unbeknownst to subjects, correct identification of one stimulus ("rich stimulus") is rewarded three times more frequently (*"Correct! You won 20 cents"*) than the other ("lean") stimulus. In healthy controls, this reinforcement schedule leads to a response bias (i.e., a preference for the more frequently rewarded stimulus). The degree of response bias toward the more frequently reinforced alternative will be used for operationalizing sensitivity to reward. This is called the "Face Game" in the consent.

*Cold Pressor Task:* Subject may be asked to participate in the Cold Pressor Task. The cold pressor task (CPT) is a stress task used to measure pain sensitivity and pain tolerance. This task will be used to determine alterations in pain thresholds as a result of endotoxin administration. Participants will immerse their hand (up to the wrist) for up to 3 minutes in the experimental (ice-cold temperature 0-4°C)) and control (room temperature (20°C)) conditions. Physiological measure (heart rate, blood pressure and subject responses (stress, mood) will be collected 5 minutes before, 1 minute into, and immediately after the CPT.

*Dot-Probe Task:* The Dot-Probe Task is used to assess attentional biases to threatening and non-threatening information. In the task the subject is instructed to fixate on a cross in the center of the screen while two stimuli, one threatening and one non-threatening are displayed on either side of the screen. The stimuli are presented for a 500 ms and then disappear, and a dot is presented in the location where of one of the stimuli used to be. The subjects are instructed to indicate the location of the dot, left or right, as quickly as possible. The reaction time to the dot when it appears in the location where the threatening stimulus had been, is interpreted as an attentional bias and increased vigilance to threat. This measure can be correlated with clinical features and outcomes of PTSD and other anxiety disorders.

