Background and Significance. Nearly 9 in 10 Americans will be exposed to trauma in their lifetimes and a significant percentage (10.1%)(22) will develop post-traumatic stress disorder (PTSD). PTSD is characterized by elevated threat (e.g., intrusions, avoidance, anxious arousal), loss (e.g., anhedonia, negative affect) and neurocognitive (e.g., verbal learning, processing speed, attention) symptoms(10, 23-31). In addition, individuals with PTSD have elevated rates of physical health morbidities(32, 33), as well as functional impairment(27, 34-36), with loss symptoms in particular contributing to a significantly decreased quality of life(28, 35-37). The immune system is responsible for maintaining health, which includes mounting a response to physical (e.g., virus, injury) and psychological (e.g., stress) insults(38-41), as well as modulating the progression of neurodegenerative conditions such as Alzheimer's disease(42, 43). All of these—physical health conditions, psychological distress, and neurodegenerative disorders—are more prevalent in individuals with than without PTSD(9, 27, 33). While the *peripheral* immune system may play a role(4, 44, 45), the role of the *neuro*immune system in PTSD has not been evaluated. We hypothesize that individuals with PTSD have a dysfunctional neuroimmune system that is chronically activated and thus over-reactive to immune challenges, which may contribute to the chronicity of symptoms. Understanding the role the neuroimmune system plays in PTSD may help identify biomarkers or "proxies" of a dysfunctional neuroimmune response, which can inform etiology and treatment of this disorder. For example, pharmacotherapies that target systems that tune the immune pathway, such as the endocannabinoid(46) or cholinergic system(47), may be evaluated for their efficacy in treating PTSD and related symptoms.

**The Neuroimmune System Modulates PTSD-Related Psychopathology.** While markers of peripheral inflammation have long been associated with a variety of psychiatric disorders, including PTSD, major depression, and addiction(1-6, 48, 49), the role that *neuro* inflammation plays is unclear. Microglia, the

Page 3 of 45

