### **Sample Size Calculation**

Power calculations were conducted by a statistician and Co-I, [name]. Preliminary data from 6 individuals with PTSD and 8 trauma-exposed controls revealed robustly higher [C]PBR28 VT values globally (21.5% higher; d=1.02) and regionally (17.3-30.1% higher; d's=0.83-1.15) in PTSD vs. controls.}} Assuming a two-sided analysis of covariance (ANCOVA) with  $\alpha$ =0.05, recruitment of 40 trauma-exposed controls and 40 individuals with PTSD (quartiles 3-4) will provide greater than 94.2% statistical power to detect effect sizes as small as d=0.80. This translates into minimum detectable differences between controls and individuals with PTSD of 15.0%. To examine relations between continuous measures of global and regional [11C]PBR28 V1 values, and measures of post-traumatic threat and loss symptoms, and neurocognitive functioning, preliminary data from 5 individuals with moderate-or-greater severity of MDD symptoms revealed a strong association between global [11C]PBR28  $V_{T}$  values and severity of loss/anhedonic symptoms (r=0.82). Further, preliminary data from 23 individuals revealed that global [ $^{11}$ C]PBR28 VT values correlated significantly with measures of learning and memory (r= -0.47) and working memory (r= -0.39). Thus, assuming a two-sided linear multiple regression model with  $\alpha$ =0.01 (0.05/5 dependent variables: dot probe and PRT scores, CAPS-5-assessed threat and loss symptoms, global cognition) and conservative overall model effect size (R^2) of .25, and up to 10 predictors, an n of 80 will provide 99.2% statistical power to detect this magnitude effect. Our previous study in 8 healthy controls revealed robust LPS-induced increases in [ $^{11}$ C]PBR28 VT values ranging in magnitude from 31% to 63%(13). We have preliminary data indicating an overall 8.8% difference (d=0.38)in global [C]PBR28 VT values between 2 individuals with PTSD and 2 matched trauma-exposed controls. Thus, assuming a minimum 8.0% differential increase in LPS-induced  $[^{11}C]PBR28 V_T$  values in the PTSD group relative to trauma-exposed controls(16),  $\alpha$ =0.05, correlation among repeated measures=0.50, and nonsphericity correction  $\varepsilon = 1$ , recruitment of 40 individuals with PTSD and 40 trauma-exposed controls will provide greater than 91.9% statistical power to detect this magnitude differential effect size.

MRI

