A univariate ANCOVA will be used to compare global [C]PBR28  $V_{T}$  values between trauma-exposed controls and individuals with PTSD. Group (Control vs. PTSD) and rs6971 genotype on the TSPO gene will be entered as fixed factors(102), variables that differ between Control and PTSD groups as additional fixed factors (categorical variables *such as major depressive disorder*) or covariates (continuous variables *such as time since index trauma*), and global [C]PBR28  $V_{T}$  values as the dependent variable. A post-hoc multivariate ANCOVA will be conducted with the same independent variables and [C]PBR28  $V_{T}$  values in individual brain regions entered as dependent variables;  $\alpha$  will be set to 0.005 (0.05/10 brain regions) in this analysis to control for Type I error. To evaluate the relation between continuously distributed global [C]PBR28  $V_{T}$  values and measures of post-traumatic threat and loss symptoms, and neurocognitive functioning, we will conduct a linear regression model using Mplus version 7.31(124). In this analysis, global [C]PBR28  $V_{T}$  values will be modeled as the independent variable, and continuously-distributed scores on objective endophenotypic measures of threat and loss symptoms, and neurocognitive functioning, and clinician interview-based measures of threat and loss symptoms will be modeled as dependent variables. Should correlation analyses reveal large magnitude associations (i.e.,  $r \ge 0.70$ ) among variables will be modeled and analyzed as latent variables.

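### The written dot-probe measure is the reaction time at the threat location, with no contrast against the non-threat location and no direction, so a score built from it would mostly reflect general response speed

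*Combined protocol and SAP*

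**What the plan says.** The Dot-Probe Task paragraph (Section I, item 4, Cognitive Measures) states the purpose: "The Dot-Probe Task is used to assess attentional biases to threatening and non-threatening information". One threatening and one non-threatening stimulus appear together, and then "a dot is presented in the location where of one of the stimuli used to be". The response is speeded: "The subjects are instructed to indicate the location of the dot, left or right, as quickly as possible". The measure is then given as: "The reaction time to the dot when it appears in the location where the threatening stimulus had been, is interpreted as an attentional bias", with increased vigilance named as the second interpretation. The next sentence takes that quantity into analysis: "This measure can be correlated with clinical features and outcomes of PTSD and other anxiety disorders".

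Two later places use the result:

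- The Sample Size Calculation sets alpha at 0.05/5 = 0.01 for five dependent variables: "dot probe and PRT scores, CAPS-5-assessed threat and loss symptoms, global cognition".
- Statistical Considerations (Section I, item 13) regresses "continuously-distributed scores on objective endophenotypic measures of threat and loss symptoms", among other outcomes, on global VT.

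Neither place gives a formula for the dot-probe score. No section subtracts the non-threat reaction time, states a direction, or adjusts the dot-probe reaction time for general speed.

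**The concern.** An attentional bias is a contrast between how quickly a person responds at two locations. The reaction time at one location is that person's general response speed plus or minus a location effect. If only the threat-location value is analysed, differences between people in general speed enter the score in full.

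The protocol itself gives a reason to expect such differences to track the disorder. The Background lists "neurocognitive (e.g., verbal learning, processing speed, attention) symptoms" among the features of PTSD, in a sample built to span the range of PTSD severity.

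The missing direction adds a second risk. Vigilance would show as a faster response at the threat location, that is, a lower reaction time. The sentence sets reaction time beside increased vigilance without saying so, and an analyst could reverse the sign.

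The dot probe is the only objective threat measure named among the five dependent variables. The regression could therefore report a VT-speed association as a VT-threat association, or miss a true VT-bias association.

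**Working it through.** **What can be checked in the documents.** No stated figure depends on how the dot probe is scored. The alpha is exact: 0.05/5 = 0.01. For comparison, the companion Probabilistic Reward Task in the same subsection is scored as a preference for one of two alternatives, which is a contrast. The dot-probe paragraph has the two conditions but uses only one.

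**Model for the size of the problem.** Let S be a subject's general reaction time and b the true bias (non-threat minus threat), with S and b independent.

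- Bias split equally: threat RT = S − b/2 and non-threat RT = S + b/2. The difference is b, and S cancels.
- Size of the correlation of threat RT with b: c = (SDb/2) / √(SDs² + (SDb/2)²). The sign is negative.
- Bias acting only at the threat location: replace SDb/2 by SDb.

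**Inputs.** n = 80 and two-sided alpha 0.01 come from the Sample Size Calculation. The following are assumptions, not in the documents: SDs 40-100 ms, SDb 10-20 ms, true VT-bias correlation 0.40, and difference-score reliability 0.3-0.7. Raw RT is treated as free of measurement error, which favours it.

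**Power formula (Fisher z).** With m = atanh(r) × √(80 − 3) = atanh(r) × 8.775, power = Φ(m − 2.576) + Φ(−m − 2.576).

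**Raw threat-location RT, true VT-bias r = 0.40.** The correlation of VT with raw RT has size 0.40 × c.

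| SDs, SDb (ms) | Bias split: c, power | Bias at threat location only: c, power |
|---|---|---|
| 100, 10 | 0.050, 1.1% | 0.100, 1.5% |
| 60, 15 | 0.124, 1.7% | 0.243, 4.3% |
| 40, 20 | 0.243, 4.3% | 0.447, 16.1% |

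Worked case, 60 and 15 ms, bias split: c = 7.5/√(3600 + 56.25) = 0.124; r = 0.0496; m = 0.436; power 1.7%. Bias then explains c² = 1.5% of the variance of raw RT.

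**Difference score, same true r = 0.40.** The observed correlation is 0.40 × √reliability.

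| Reliability | Observed r | Power |
|---|---|---|
| 0.7 | 0.335 | 68% |
| 0.5 | 0.283 | 49% |
| 0.3 | 0.219 | 27% |

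**No VT-bias link, VT related only to speed.** The documents give no VT-speed correlation, so a range is shown. Here r is the correlation of VT with raw RT, which over this grid is nearly the correlation with speed because c is small.

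| r | Raw RT significant at 0.01 |
|---|---|
| 0 | 1% |
| 0.1 | 5% |
| 0.2 | 21% |
| 0.3 | 56% |

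Speed cancels in the difference score under this model, so its rate stays at the nominal 1%.

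**The case against.** The strongest reply is that the paragraph is a lay description. Item 4 asks for non-technical language, and the sentence says how a reaction time is interpreted, not which variable will be entered in a model. The stated purpose is comparative, the dot can replace either stimulus, and the later sections speak of scores. A difference score may well be what the investigators have in mind. This stands, and it is why the point concerns the written definition. It does not remove the point, because that sentence is the only definition and an analyst who follows it gets a speed-dominated score.

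A reader might infer more than the documents support in four ways:

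- *That the measure captures slowness and not vigilance.* Raw RT mixes the two. Speed dominates under the assumed SDs, but that rests on assumptions.
- *That false threat findings would be the usual result.* This needs a sizeable VT-speed correlation. The pilot correlation of −0.39 in the Preliminary studies is with working memory, not speed, and cannot be borrowed.
- *That the LPS-change and mediation analyses are affected.* Those paragraphs of Statistical Considerations do not name the dot probe. Cognitive Measures says only that measures may be taken on PET days, and the payment section lists the dot probe under baseline assessments. Stable differences in speed would also largely cancel in a within-person change.
- *That slowing in PTSD would be read as reduced vigilance in a group test.* No PTSD-versus-control comparison of dot-probe scores is specified; the planned analysis is a regression on VT.

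The advantage of the difference score should not be overstated either. An error-free bias score would have 87% power, but no such score can be collected; 27%-68% is the fairer comparison.

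**Conclusion.** The concern holds as a defect in the written definition: no contrast, no direction, and no scoring rule elsewhere to supply them. If the definition is followed, the dot-probe regression on global VT has about 1%-4% power for a true VT-bias correlation of 0.40, or up to 16% if bias acts only on threat-location RT. It would also be significant in about 1% to 56% of trials when VT is related to speed alone at r = 0 to 0.3. These figures rest on the assumed SDs, on independence of speed and bias, and on the assumed correlations. The ordering of the two scores is the same across the whole range shown.

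The reach is limited. This is one of five dependent variables, CAPS-5 threat symptoms are a separate threat measure in the same family, and the primary VT comparison between groups does not use the dot probe. The change should be made before analysis, but it does not threaten the main result.

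**What to change.** In the Dot-Probe Task paragraph, replace the sentence that interprets the threat-location reaction time with a definition such as:

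*Bias score = mean reaction time on correct trials with the dot at the non-threat location, minus mean reaction time on correct trials with the dot at the threat location. Positive values indicate vigilance to threat; negative values indicate avoidance.*

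State in the same place how outlying reaction times are handled. Name this score as the dot-probe dependent variable in the Sample Size Calculation and in the regression paragraph of Statistical Considerations. Carry it into the LPS-change and mediation paragraphs only if the task is repeated after LPS, and say whether it is.

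The cost is protocol wording. The dot appears at one or other stimulus location, so the comparison trials appear to be collected already, and alpha and sample size do not change. The downside is that a difference score is less reliable than a raw reaction time, which is the loss shown in the 27%-68% range.

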### **Image Analysis**

### Outcome Measure and Dependent Variables

For PBR28, the primary outcome measure is total volume of distribution ( $V_T$ ) which is proportional to *in vivo* TSPO levels. There is no brain region that does not exhibit specific binding of PBR28. Thus, for full quantification of  $V_T$ , arterial sampling is required. We will examine the regions-of-interest (ROIs) listed below. For PBR28 we will use two-tissue compartmental analyses with a metabolite-corrected arterial input function to estimate total distribution volumes for each ROI (117).

### MRI-Based ROI Definition

We will use the MR image to define regions of interest (ROIs). The PET scans alone do not have sufficient resolution to identify brain regions. The PET image sets are aligned and resliced to yield images in the same planes and spatial system as the MRI images using AAL template. Primary ROIs will include the hypothalamus, thalamus, amygdala, striatum, and the cingulate and frontal cortices. Other ROIs will be examined *post hoc* to assess radiotracer binding.

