In Aim 1, we will determine whether individuals with PTSD have higher levels of activated microglia compared to trauma-exposed control subjects as measured with [C]PBR28 PET brain imaging. Eighty subjects (n=40 with a primary diagnosis of PTSD; n=40 trauma-exposed controls) will participate in a [C]PBR28 PET scan to assess baseline levels of activated microglia. We will perform clinical assessments and measure cytokine levels, mood, anxiety and neurocognitive function on PET scan day. *Based on our preliminary data, we hypothesize that individuals with PTSD will have higher levels of neuroinflammation compared to trauma-exposed healthy controls, particularly in the amygdala, hippocampus, ventral striatum and frontal cortex, and that higher levels of neuroinflammation will be associated with greater severity of mood and anxiety symptoms and neurocognitive dysfunction.* 

In Aim 2, we will use our novel neuroinflammation "stress test" to determine whether individuals with PTSD vs. trauma-exposed controls have a dysfunctional neuroinflammatory response to systemic administration of LPS. The same subjects from Aim 1 will be administered LPS 3 h prior to a second [C]PBR28 PET scan on the same day, consistent with our established paradigm(13). Cytokine and cortisol levels, mood and anxiety symptoms, and neurocognitive function will be assessed pre- and post-LPS administration. *We hypothesize based on preclinical studies(16) that, compared to controls, individuals with PTSD will have an exacerbated neuroimmune response to LPS evidenced by greater increases in activated microglia. We further expect that greater LPS-induced increases in activated microglia will be associated with greater increases in cortisol levels, mood and anxiety symptoms, and reductions in neurocognitive function.* 

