Administration. Preclinical studies using a psychological stressor, namely chronic restraint stress, document a robust increase in microglial activation, both in number(86, 87) and in morphology(87). Another model of psychological stress – inescapable shock (IS) - also led to neuroinflammation(88), and the drug minocycline, which inhibits microglial activation, reduced the shock-induced neuroinflammatory response(89). Most importantly, there is evidence that psychological stress (i.e., inescapable shock) can activate microglia, which then sensitizes the pro-inflammatory reactivity of microglia to subsequent immune challenges(16). There is crosssensitization between stress and peripheral proinflammatory cytokine responses(90), and exposure to a stressor can sensitize LPS-induced cytokine

[figure not shown]

[figure not shown]
Figure 1. Effect of inescapable shock (IS) on the microglia proinflammatory response to LPS ex vivo. Hippocampal microglia were isolated from HCC and 24 h post-IS and exposed to LPS. Gene expression of the pro-inflammatory cytokine IL-1 $\beta$  was then measured. IS significantly potentiated the pro-inflammatory response of microglia to LPS compared to HCC (N=5/group). HCC LPS vs. IS LPS. \*p<0.05

production(91). One study in particular helps form the basis for our hypothesis for Aim 2. Frank and colleagues(16) found that inescapable shock robustly increased activated microglia and potentiated the pro-inflammatory response to LPS in the hippocampus; **Figure 1**). In other words, stress primed the microglia and they became hyper-reactive to subsequent immune challenges. In **Figure 1**, black bars show the increase in IL-1beta gene expression—a protein found on activated microglia—in the hippocampus, and white bars show the media control. HCC are the home cage controls that received no shock and do have a robust neuroimmune response to LPS like healthy humans in our study(13). We hypothesize that individuals with PTSD have a much larger response to LPS, which is analogous to the group that received inescapable shock (IS) 24 hours prior to the LPS challenge. Thus, we hypothesize that individuals with PTSD will have an exacerbated neuroinflammatory response to an LPS challenge compared to controls. Our overall hypothesis is that chronic stress leads to chronically higher levels of neuroinflammation (Aim 1), which primes the system to respond excessively to an immune challenge (Aim 2).

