Linear mixed-effects models will be used to compare LPS-induced changes in [C]PBR28  $V_T$  values in the Trauma Control and PTSD groups. Group (Control vs. PTSD) and rs6971 polymorphism in the TSPO gene will be entered as fixed factors, subject as a random effect, pre-LPS global [C]PBR28  $V_T$  values as a covariate, and post-LPS global [C]PBR28  $V_T$  values as the dependent variable; variables that differ between Trauma Control and PTSD groups will be entered as additional fixed factors (categorical variables) or covariates (continuous variables). An ANCOVA with the rs6971 polymorphism in the TSPO gene and other variables that differ by PTSD status entered as covariates will be conducted to compare %change in [C]PBR28  $V_T$  values in the PTSD vs. Trauma Control group. Post-hoc analyses adjusted for multiple comparisons ( $\alpha$ =0.005; 0.05/10 brain regions) will be conducted to evaluate LPS-induced changes in [C]PBR28  $V_T$  values in individual brain regions in these two groups. Interrelationships among changes in outcome measures will be evaluated in the full sample and by PTSD group status using parallel process analyses in Mplus version 7.31.

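### The primary ROI list leaves out the hypothesised hippocampus and does not separate ventral striatum, and the ten regions behind the regional alpha of 0.005 are never named

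*Combined protocol and SAP*

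**What the plan says.** Three places bear on this point.

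- **Statement of Purpose, Aim 1** places the expected group difference "particularly in the amygdala, hippocampus, ventral striatum and frontal cortex": four regions. The Background section rests the Aim 2 hypothesis largely on an animal study in which prior shock "potentiated the pro-inflammatory response to LPS in the hippocampus".
- **Image Analysis, MRI-Based ROI Definition** gives six regions: "Primary ROIs will include the hypothalamus, thalamus, amygdala, striatum, and the cingulate and frontal cortices". The next sentence begins "Other ROIs will be examined" and makes that examination post hoc. It gives neither the number nor the names of these other regions.
- **Item 13, Statistical Considerations** tests global V_T first. For the regions in Aim 1, "A post-hoc multivariate ANCOVA will be conducted with the same independent variables", and alpha "will be set to 0.005 (0.05/10 brain regions) in this analysis to control for Type I error". The Aim 2 regional tests, also called post hoc, use the same 0.005. The ten regions are not listed there or elsewhere.

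The Sample Size Calculation reports preliminary regional effects of d=0.83 to 1.15. It gives power for the Aim 1 group comparison only at alpha 0.05.

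**The concern.** The regional hypothesis, the primary ROI list and the multiplicity correction imply three counts: four, six and ten. They do not map onto one another.

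Two things are at stake. First, a difference in hippocampus, which Aim 1 predicts, would come from a region outside the primary list and so carry less weight than the hypothesis intends. A difference confined to ventral striatum would be averaged into the whole striatum. Second, because the ten are unnamed, no reader can check that the divisor matches what was tested, and the family could be settled after the data are seen. The plan also gives no regional power at the alpha it will use.

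**Working it through.** **1. Setting the lists side by side**

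| Region | Aim 1 hypothesis | Primary ROI list |
|---|---|---|
| Amygdala | yes | yes |
| Frontal cortex | yes | yes |
| Hippocampus | yes | no |
| Ventral striatum | yes | only within whole striatum |
| Hypothalamus, thalamus, cingulate | no | yes |

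One hypothesised region is missing and one is not separated. The count used for alpha is ten.

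**2. Reproducing the plan's power**

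Inputs from the Sample Size Calculation: n=40 per group, d=0.80, two-sided alpha 0.05.

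- Noncentrality = d × √(n/2) = 0.80 × √20 = 3.578.
- With 78 degrees of freedom the critical t is 1.991, and power is 94.2%. This is the plan's figure.
- Allowing one covariate (77 degrees of freedom) also gives 94.2%.

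**3. Power per region at the regional alpha**

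The formula is the same, with 77 degrees of freedom and alpha = 0.05/m. The effect sizes are the d=0.80 of the power statement and the two ends of the preliminary regional range.

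| Regions m | alpha | d=0.80 | d=0.83 | d=1.15 |
|---|---|---|---|---|
| 4 | 0.0125 | 84.3% | 87.3% | 99.5% |
| 6 | 0.0083 | 80.5% | 83.9% | 99.2% |
| 10 | 0.005 | 75.1% | 79.1% | 98.6% |

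At d=0.80, dividing by ten costs 80.5 − 75.1 = 5.4 points if six regions are tested, and 84.3 − 75.1 = 9.2 points if four are. If ten are tested, the divisor itself wastes nothing by the Bonferroni rule.

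**4. Family-wise error at 0.005 per test**

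The Bonferroni bounds are 10 × 0.005 = 0.05, 6 × 0.005 = 0.03 and 4 × 0.005 = 0.02.

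Statistical Considerations reports correlations above 0.80 between regional V_T values. For ten tests I simulated equicorrelated normal statistics, Z_j = √r·W + √(1−r)·E_j, with W and E_j independent standard normal, and counted how often any |Z_j| passed the two-sided 0.005 limit.

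| Assumed r | Family-wise error, ten tests |
|---|---|
| 0.5 | about 3.9% |
| 0.8 | about 2.3% |
| 0.9 | about 1.6% |

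At r=0.8, a method that uses the correlation would allow about 0.012 per test over ten regions instead of 0.005.

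**The case against.** The strongest reply has four parts.

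- **The regional analysis is already post hoc.** The tests that carry Aims 1 and 2 use global V_T. Under item 13 an amygdala result has the same post hoc label as a hippocampal one. This stands, and it limits the point to the regional analyses. It does not explain why the plan has a primary ROI list that leaves out a region its own hypothesis names.
- **Ventral striatum is not left out.** It lies inside the listed striatum. This stands: the loss is possible dilution and the lack of a separate estimate.
- **Ten may really be tested.** The ROI section allows other regions, so six plus four more, hippocampus among them, would fit the divisor. This is possible, and then 0.05/10 is correct Bonferroni. The plan does not say so, and that gap is the defect.
- **The figures depend on assumptions.** The power figures treat each region as a univariate comparison, whereas the plan has a multivariate ANCOVA with genotype and other factors. The reported correlations may be unadjusted for genotype, and the genotype's roughly two-fold effect on V_T would inflate them. This stands, and it is why ranges are given. Bonferroni remains valid; its conservatism is an inefficiency, not an error.

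A reader might also infer that the sponsor's other primary regions should be demoted. The documents do not support that. Aim 1 says particularly, not only; the Background cites raised binding in the anterior cingulate in depression and proposes an HPA-axis mechanism.

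**Conclusion.** The inconsistency is real and should be corrected before analysis. Hippocampus is hypothesised but is not a primary ROI, ventral striatum has no estimate of its own, and the regional family behind 0.05/10 is undefined for both aims.

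Regional power at the planned alpha is about 75% at d=0.80 and 79% at d=0.83, well below the quoted 94.2%; at d=1.15 it is about 99%, and the choice of divisor hardly matters. The cost of dividing by ten, about 5 or 9 points at d=0.80, arises only if six or four regions are tested.

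Two stronger readings are tempting and are not supported. One is that the regional tests miss the stated question: two of the four hypothesised regions are listed outright, a third is contained in a listed one, and hippocampus may be among the ten. The other is that power is lost whatever is tested, or that the main conclusions are at risk: the loss from the divisor is conditional, and the global tests do not depend on it.

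These figures assume 40 analysable subjects per group, d as the covariate-adjusted effect, one test per region, and equal correlation between regions for the error rates.

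**What to change.** 1. In MRI-Based ROI Definition, add hippocampus to the primary ROIs. Add ventral striatum as well if the MRI/AAL pipeline can delineate it, which the documents do not show; otherwise reword the Aim 1 hypothesis to whole striatum. Keep the six existing regions.
2. Name that list as the regional family and use it for the regional tests in both Aim 1 and Aim 2. Mark any other region as exploratory.
3. In Statistical Considerations, replace the fixed 0.05/10 in both places with Holm or a permutation max-statistic over the named family. The latter takes account of the correlation between regions.
4. In the Sample Size Calculation, state regional power at the resulting alpha. With both regions added the family has 6 + 2 = 8 members. The first Holm step is then 0.05/8 = 0.00625, where power is 77.5% at d=0.80 by the formula above.

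The cost is a wording change and slightly more analysis work, with no new scans or visits. The plan would also have to show a regional power figure lower than the 94.2% quoted at alpha 0.05.
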